The second condition will be psychoeducational (i.e., the control condition). Participants randomly assigned to the control condition will receive links to websites that provide general psychoeducation about alcohol (e.g., <https://www.niaaa.nih.gov/publications/brochures-and-fact-sheets>), and mental illness (e.g., <https://www.jack.org/resources>). Therefore, the control group will have access to available online psychoeducational material. A psychoeducation control group is common in clinical research in order to determine the efficacy and effectiveness of online interventions (Schaub et al., 2016). It is also important as we do not want to harm patients in any way or prevent them from getting something that is already established are effective. For ethical reasons, participants in the psychoeducation control group will be given access to the active integrated treatment at the end of the study, regardless of whether they have completed all of the assessments.

*Research Instruments:* Participants will be assessed at three time points throughout the study: at baseline (i.e., prior to treatment; T0), immediately following the 8-week treatment (T1), and at follow-up (i.e., 24 weeks, T2). The primary outcome of interest will be the number of standard drinks consumed during the seven days prior to the assessment. This will be assessed using the Timeline Follow-Back (TLFB; Sobell & Sobell, 1992) procedure at all assessment points (T0-T2). The TLFB has been widely used in studies, including treatment studies (Keough, O'Connor, & Colder, 2016; Schaub et al., 2016). As a secondary outcome, depressive symptoms will also be assessed at all time points using the CES-D, a 20-item self-report questionnaire used to indicate

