depression severity (Radloff, 1977). Anxiety symptoms will also be assessed at all three assessment points using the GAD-7, a 7-item self-report questionnaire used to measure the severity of anxiety symptoms (Spitzer, Kroenke, Williams, & Löwe, 2006). In order to determine clinically significant and combined reduction in alcohol use and comorbid emotional problems, we will use a combined outcome of alcohol use on the AUDIT, and cut-offs from the GAD-7 and CES-D. We will also measure participants' quality of life using the World Health Organization Quality of Life assessment (WHOQOL-BREF). This is a 26-item self-report measure that assesses functionality in various life domains (The WHOQOL Group, 1998). A sum score will be used to assess overall quality of life at all assessments points (i.e., T0-T2). We will also collect information on participants' use of other substances using the National Institute on Drug Use (NIDA ASSIST; National Institute on Drug Abuse, 2009), and their executive functioning using the WebEx (Buchanan et al., 2010). This information will be collected to examine transfer effects to other substances, as well as to examine the potentially moderating effects of executive functioning. Finally, we will obtain a measure of participants' level of motivation in terms of importance, confidence, and readiness. Participants will complete all measures at each of the three time points, with the exception of the Demographics questionnaire and the AUDIT, which will only be completed at baseline.

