## **Participants**

A target sample of 400 participants will be recruited for the study. Participants will include Canadian young adults struggling with moderate alcohol misuse and emotional problems. Inclusion criteria will include: 1) individuals between 18 and 35 years old, 2) reporting difficulties with alcohol indicated by a score  $>3$  for women and  $>4$  for men on a brief version of the Alcohol Use Disorders Identification Test [AUDIT; Saunders et al., 1993] known as the AUDIT-C, 3) reporting depression and/or anxiety symptoms indicated by a score  $>16$  on the Center for Epidemiological Studies Depression Scale [CES-D] and/or a score of  $>5$  on the Generalized Anxiety Disorder Scale-7 [GAD-7], 4) fluency in English, and 5) have weekly Internet access. Exclusion criteria will include the following: 1) self-reported engagement in other psychological or pharmacological treatments for alcohol misuse and/or depression/anxiety; 2) elevated suicidality (defined as scoring greater than "minimal risk" on a screener); and 3) current psychosis or mania. Interested participants will be invited to contact the primary investigators for a link to the study website. Participants will be sent a link with information about the study and be able to provide informed consent electronically directly on the treatment website. They will also be provided with detailed instructions on how to create a user account for the self-help program, and be encouraged to contact the researchers should they have any trouble at this stage. After they have provided informed consent, they will be able to register on the study website. They will need to create a username as well as verify their account via e-mail before they can access the website. After informed consent has been obtained and their account has been verified, they will immediately be asked to complete the baseline assessment measures. If they are eligible, they will be able to access the 12 treatment modules and continue with the study procedure. Interested adults with clinically-elevated symptoms (i.e., those who score above the cut-offs on our screening tools) will be still given access to the integrated intervention, and will be given the contact information for a mental health professional in their area. However, they will be excluded from the study and their data will not be tracked.

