## Statistical Analysis Plan

**Power Analysis:** A recent meta-analysis showed that combined CBT/MI resulted in statistically significant reductions in alcohol use and depressive symptoms, with effect sizes being in the small range in both clinical and subclinical groups ( $g=.17-.27$ ). Data show relatively comparable effect sizes for online and in person interventions for alcohol misuse and depression. Therefore, a small effect size ( $g=.25$ ) is expected for group differences in alcohol use and emotional symptoms at posttreatment. Using G\*Power, the required sample size to detect a small effect size is  $N=398$  (with power rate set at .80 and  $\alpha = .05$ ).

**Statistical Plan:** Before hypothesis testing, we will run preliminary analyses (e.g., baseline differences, missing data analyses). We will also examine overall group differences in clinically meaningful variables (i.e., % below moderate cut-offs on the AUDIT, CES-D, and GAD-7 after treatment and at follow-up). Next, Generalized Estimating Equations (GEE) will be used to evaluate the main hypotheses that integrated treatment will result in the largest reductions in alcohol use, depression, and anxiety. GEE is a multilevel modeling technique that is preferable to repeated-measures ANOVA for pre/post analyses, as it will allow us to include all randomized participants in analyses. This results in less bias due to missing follow-up data. However, due to potential attrition problems, we also plan to conduct a sensitivity analysis. Primary and secondary outcomes will be tested sequentially in a mixed within- (repeated assessments) and between-subjects (treatment condition) design.

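### The AUDIT is given at baseline only, yet the SAP compares the arms on an AUDIT cut-off at T1 and T2 and the protocol's combined outcome depends on it

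*Protocol*

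**What the plan says.** Three statements in the current text bear on this.

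- **Schedule (Protocol, Method, Research Instruments).** The general rule is that "Participants will complete all measures at each of the three time points". Two instruments are then taken out of that rule: "with the exception of the Demographics questionnaire and the AUDIT, which will only be completed at baseline". The time points are baseline (T0), the end of the 8-week treatment (T1) and 24 weeks (T2).
- **Combined outcome (same paragraph of the protocol).** To identify a clinically significant joint reduction in drinking and emotional problems, "we will use a combined outcome of alcohol use on the AUDIT, and cut-offs from the GAD-7 and CES-D".
- **Analysis (SAP, Statistical Plan).** "We will also examine overall group differences in clinically meaningful variables", specified as the percentage "below moderate cut-offs on the AUDIT, CES-D, and GAD-7 after treatment and at follow-up".

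Two further places matter for the interpretation. The Participants section sets the alcohol inclusion criterion "on a brief version of the Alcohol Use Disorders Identification Test", the AUDIT-C, with thresholds of >3 for women and >4 for men. The primary outcome, standard drinks over the previous seven days by TLFB, is collected at T0, T1 and T2.

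**The concern.** A percentage below a cut-off after treatment, or a reduction from baseline, needs a post-baseline score. The protocol explicitly excludes the AUDIT from the post-baseline assessments; this is a stated exception and not a gap in a schedule. The schedule therefore cannot stand together with either the SAP comparison or the combined outcome.

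The loss would be permanent, because an AUDIT not given at T1 or T2 cannot be recovered later. If the problem came to light only at analysis, the team would have to drop a planned comparison or choose a substitute alcohol threshold with outcome data already in hand. The combined outcome is also the protocol's own measure of clinically significant change in both problems together, and treating both at once is the rationale for the intervention.

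**Working it through.** The plan gives no figure on this point to reproduce, and the sample-size calculation does not involve the AUDIT. The check is a comparison of what is scheduled with what is to be analysed.

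**Inputs**

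- Time points: 3 (T0, T1, T2), Protocol, Research Instruments.
- Target sample: 400, Protocol, Participants.
- Scales in the SAP cut-off comparison: 3 (AUDIT, CES-D, GAD-7), at 2 time points.
- Components of the combined outcome: 3 (AUDIT, GAD-7, CES-D).

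**Step 1: scheduled against required**

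| Scale | Scheduled at | Required by the SAP comparison at | Data at T1 and T2? |
|---|---|---|---|
| CES-D | T0, T1, T2 | T1, T2 | Yes |
| GAD-7 | T0, T1, T2 | T1, T2 | Yes |
| AUDIT | T0 only | T1, T2 | No |

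**Step 2: AUDIT scores available at the target, assuming full follow-up**

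- Possible: 400 × 3 = 1,200.
- Scheduled: 400 × 1 = 400, all at T0.
- Scheduled at T1 and T2: 0 of 400 × 2 = 800.

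Attrition would reduce the 800 but would not change the zero.

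**Step 3: SAP cut-off comparisons affected**

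The SAP does not say whether the three percentages are separate or joint, so both readings are shown.

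- Separate percentages: 3 scales × 2 time points = 6 comparisons. The AUDIT accounts for 1 × 2 = 2, which have no data. The other 2 × 2 = 4 can be made.
- One joint percentage below all three cut-offs: 1 × 2 = 2 comparisons, and neither can be made.

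**Step 4: combined outcome**

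At each of T1 and T2, 2 of 3 components are scheduled. The missing one is the only alcohol component. If the outcome requires all three, it cannot be evaluated at all after baseline. If some other rule is meant, what remains describes mood and anxiety only. The protocol does not state the rule.

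**Step 5: does another place supply the data?**

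Neither document schedules the AUDIT at T1 or T2, or schedules the AUDIT-C by name after baseline. The AUDIT-C is named only as an inclusion criterion. The TLFB is repeated, but it counts drinks over seven days and the documents set no TLFB cut-off, so as defined it does not yield a percentage below a threshold.

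**The case against.** The best counter-argument is that the AUDIT-C is what is meant. The baseline-only exception names the AUDIT, all other measures are repeated, and the protocol introduces the AUDIT-C as a short form of the AUDIT. If the AUDIT-C is repeated and the SAP uses the longer name loosely, the fault is one of naming and not of missing data. This cannot be excluded, but it is the weaker reading: the protocol names the AUDIT-C only for eligibility, and both the combined outcome and the SAP say AUDIT. Even if it is right, the text needs correcting, because the short form would have to be scheduled by name and given its own cut-off.

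A second point is that the combined outcome and the SAP's cut-off comparison use the same three scales and may be one analysis described twice. That is possible. The losses in Steps 3 and 4 should therefore not be added together as if they were certainly distinct.

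A third point is that the consequence is limited, and this stands. The SAP places the cut-off comparison before hypothesis testing, and it is only afterwards that "Generalized Estimating Equations (GEE) will be used to evaluate the main hypotheses". It does not name the combined outcome. Change in drinking is still measured by the TLFB at all three time points.

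Finally, one might ask whether an AUDIT repeated after 8 weeks would be interpretable. The documents give no recall period for the instrument, so this cannot be judged from them.

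**Conclusion.** The concern holds. As written, the plan calls for post-baseline AUDIT results from an instrument that it gives only at baseline. Either 2 of 6 cut-off comparisons (separate scales) or 2 of 2 (joint criterion) have no data, and the combined outcome lacks its only alcohol component at T1 and T2.

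This rests on reading AUDIT as the instrument named. It assumes no response rate and no particular rule for combining the components.

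The effect is confined to supporting results. The TLFB primary outcome, the CES-D and GAD-7 outcomes, the GEE models and the power calculation are untouched. It should be fixed because the loss is irreversible and the correction is cheap. Separately, the SAP gives no numerical value for the moderate cut-off on any of the three scales; the conclusion does not depend on that gap.

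**What to change.** Either of two changes resolves the conflict.

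**(a) Collect the data.** Remove the AUDIT from the baseline-only exception in Research Instruments and give it online at T1 and T2. If the AUDIT-C is intended, schedule it by name there, name it in the combined outcome and in the SAP, and state its own cut-off. The cost is one short questionnaire at two existing online assessments, plus wording. It must be settled before the first T1 assessment.

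**(b) Keep the schedule and redefine the outcome.** Drop the post-baseline AUDIT comparison from the SAP. In both documents, base the alcohol component on the TLFB seven-day drinks already collected, with a threshold fixed before outcome data are seen. This adds no participant burden and needs wording only, but the construct becomes recent consumption, and the plan should say so.

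The documents do not show whether T1 assessments have begun. If they have, (a) would leave the earliest participants without T1 scores, while (b) remains available as long as outcome data have not been seen.

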## **Participants**

A target sample of 400 participants will be recruited for the study. Participants will include Canadian young adults struggling with moderate alcohol misuse and emotional problems. Inclusion criteria will include: 1) individuals between 18 and 35 years old, 2) reporting difficulties with alcohol indicated by a score  $>3$  for women and  $>4$  for men on a brief version of the Alcohol Use Disorders Identification Test [AUDIT; Saunders et al., 1993] known as the AUDIT-C, 3) reporting depression and/or anxiety symptoms indicated by a score  $>16$  on the Center for Epidemiological Studies Depression Scale [CES-D] and/or a score of  $>5$  on the Generalized Anxiety Disorder Scale-7 [GAD-7], 4) fluency in English, and 5) have weekly Internet access. Exclusion criteria will include the following: 1) self-reported engagement in other psychological or pharmacological treatments for alcohol misuse and/or depression/anxiety; 2) elevated suicidality (defined as scoring greater than "minimal risk" on a screener); and 3) current psychosis or mania. Interested participants will be invited to contact the primary investigators for a link to the study website. Participants will be sent a link with information about the study and be able to provide informed consent electronically directly on the treatment website. They will also be provided with detailed instructions on how to create a user account for the self-help program, and be encouraged to contact the researchers should they have any trouble at this stage. After they have provided informed consent, they will be able to register on the study website. They will need to create a username as well as verify their account via e-mail before they can access the website. After informed consent has been obtained and their account has been verified, they will immediately be asked to complete the baseline assessment measures. If they are eligible, they will be able to access the 12 treatment modules and continue with the study procedure. Interested adults with clinically-elevated symptoms (i.e., those who score above the cut-offs on our screening tools) will be still given access to the integrated intervention, and will be given the contact information for a mental health professional in their area. However, they will be excluded from the study and their data will not be tracked.

Participants will be recruited both in-person (e.g., presentations, posters) and online through university clinics, community agencies, online advertisements (e.g., Google Ads, Kijiji), social media, and word of mouth. All participants who request it will receive a summary of the study results once the study is complete. These summaries will debrief participants about the main goal of the study. Furthermore, all participants will be offered the option of receiving an electronic summary of the study results after it is complete. This summary will be sent to participants by email.

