Participants will have 8-weeks to complete the modules and will immediately be given access to all modules. While it is technically possible to work through the modules in any order, they will be encouraged to work through the modules sequentially. In order to bring a small social presence to the treatment, each module will begin with a brief introduction video. Previous research suggests that adding this social factor will personalize the online program and may influence accountability (Mohr, Cuijpers, & Lehman, 2011), especially considering that it is self-guided. The purpose of these videos will be to summarize the content of the upcoming module, as well as provide motivation to continue with the program. Participants will also be supported by an e-coach during active treatment. This coaching content will all be automated, with the exception of specific questions participants may have for their e-coach. They will be able to ask these questions over e-mail. The purpose of the e-coach will be to answer any questions the participant may have as they work their way through the modules. Coaches will provide ongoing feedback about module progress and provide reminders about completing each section of the intervention. They will also provide support to participants should have they additional questions or concerns throughout the program. Therefore, the use of e-coaches will help to reduce the risk of attrition. Research shows that both automatic and personal feedback are central to improving adherence during self-guided behaviour change interventions (Mohr et al., 2011). At the outset of treatment, participants will also be asked to select an animated personal companion whom they identify with in terms of sex, age, occupation, and family background. The purpose of this companion is to provide advice and examples pertaining to the content throughout the intervention. The personal companion will appear in each module at least once.

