### **Compensation**

Participants will be compensated with a \$30 Amazon gift card for completing all three assessments (\$10 per assessment).

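### The enrolment target of 400 is the SAP's required 398 plus two, with no stated allowance for missing T1 data, so for an unadjusted T1 comparison the stated power of .80 does not hold at 400 enrolled once T1 data are lost

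*Protocol*

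**What the plan says.** The SAP's power paragraph assumes a standardised effect of g=.25, which "is expected for group differences in alcohol use and emotional symptoms at posttreatment". With power .80 and alpha .05 it concludes that "the required sample size to detect a small effect size is" 398. It cites G\*Power but names neither the test nor whether it is one- or two-sided. The protocol's Participants section then sets enrolment: "A target sample of 400 participants will be recruited for the study". Allocation is 1:1 (protocol, Method).

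The documents do address missing data in the analysis and in the conduct of the trial:

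- SAP, statistical plan: before hypothesis testing, "we will run preliminary analyses (e.g., baseline differences, missing data analyses").
- SAP, statistical plan: GEE is preferred because "it will allow us to include all randomized participants in analyses".
- SAP, statistical plan: "However, due to potential attrition problems, we also plan to conduct a sensitivity analysis".
- Protocol, Method: "the use of e-coaches will help to reduce the risk of attrition". This may refer to dropout from the programme rather than from assessment.
- Protocol, Compensation: payment is $10 per assessment, as a "gift card for completing all three assessments".

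Neither document gives an expected dropout or retention rate, an inflation step, or a correlation between baseline and T1.

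**The concern.** The expected effect is a group difference at the 8-week assessment, so the information that drives the calculation is the T1 outcome. A required N computed without a dropout term is a number of participants with that outcome, not a number to enrol. Here the two are nearly the same (398 and 400), in a self-guided online programme where the SAP itself foresees attrition.

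What is at stake is the power figure, not the validity of the comparison. If power at the real observed N is well below .80, a non-significant result would be read against a sensitivity that the trial did not have.

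**Working it through.** **Inputs.** From the SAP power paragraph: d=.25, alpha=.05, target power .80, N=398. From the protocol: 400 enrolled, 1:1 allocation. Assumed, because the documents are silent: loss of T1 data of 0 to 30%, equal in both arms; sidedness; baseline–T1 correlation r.

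**Step 1: reproduce 398.** For two equal arms with total N, the noncentrality is d·√(N/4) on N−2 degrees of freedom, and power is the upper tail of the noncentral t beyond the critical value.

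- One-tailed, N=398: noncentrality .25·√99.5 = 2.494, critical t = 1.649, power .8008.
- One-tailed, N=396: power .7991. So 398 is the smallest even N that reaches .80, with no dropout term.
- Two-sided, unadjusted: N=504 gives .7998 and N=506 gives .8014. The minimum is 506, so 398 does not reproduce.

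The one-tailed t-test is the simplest route to 398, but not the only possible one. A two-sided ANCOVA (effect d/√(1−r²), N−3 degrees of freedom) also gives 398 if r is about .46. No document states such a correlation.

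**Step 2: margin.** 400 − 398 = 2, and 2/400 = 0.5%. The target therefore absorbs the loss of two T1 outcomes.

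**Step 3: power with 400 enrolled and T1 data lost, unadjusted comparison.** Observed N = 400·(1 − loss).

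| T1 loss (assumed) | Observed N | One-tailed | Two-sided |
|---|---|---|---|
| 0% | 400 | .803 | .703 |
| 5% | 380 | .784 | .681 |
| 10% | 360 | .765 | .657 |
| 20% | 320 | .721 | .606 |
| 30% | 280 | .671 | .550 |

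**Step 4: what baseline adjustment could recover.** Same calculation, one-tailed, with the effect scaled to d/√(1−r²).

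| T1 loss (assumed) | r=.3 | r=.5 |
|---|---|---|
| 0% | .834 | .892 |
| 5% | .817 | .878 |
| 10% | .799 | .862 |
| 20% | .756 | .824 |
| 30% | .706 | .778 |

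The minimum observed N for .80 falls from 398 (r=0) to 362 (r=.3) or 300 (r=.5). From 400 enrolled, that tolerates a loss of 38/400 = 9.5% or 100/400 = 25%.

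If 398 came instead from the two-sided ANCOVA with r=.46, the adjustment is already spent. Power is then .802, .782, .759, .709 and .651 at 0, 5, 10, 20 and 30% loss.

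**The case against.** The best defence is that the planned analysis is not a posttest-only t-test. The SAP specifies a repeated-measures GEE that uses baseline and keeps every randomised participant, and the protocol has three assessments. The t-test may have been a deliberately simple and conservative basis. On that view the efficiency of the planned model is an unstated reserve: with a one-tailed test and r=.5, power stays above .80 at 20% loss. Attrition is also not ignored, given the missing-data analyses, the sensitivity analysis, the e-coach support and the payment per assessment.

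Much of this stands, and it rules out two stronger readings. A reader might infer that .80 is reached only if almost everyone enrolled provides T1 data. The documents do not support that as a general statement: it is true of an unadjusted comparison, but Step 4 shows that a moderate baseline correlation could cover a loss of 9.5% or 25%. A reader might also infer that missing T1 data cost the same power whatever calculation lies behind 398. That does not follow either. In a test of the group difference averaged over assessments, a participant who misses T1 still contributes the other measures, and the cost would be much smaller.

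What does not stand is the step from these possibilities to the stated .80. The SAP gives no correlation and claims no credit for adjustment or repeated measures, and it ties the effect to posttreatment. Including all randomised participants keeps them in the model but does not supply the T1 outcomes they did not give. Retention measures may reduce loss, but no retention figure follows from them.

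**Conclusion.** The point holds as a missing assumption, not as an arithmetic slip: 398 reproduces, and 400 exceeds it. Neither document states an attrition allowance, and the margin of two (0.5%) cannot serve as one. For an unadjusted one-tailed comparison at T1, power at 400 enrolled falls from .803 to .765 at 10% loss and .721 at 20%. If the test is two-sided and unadjusted, it is .703 before any loss and .606 at 20%, so the undeclared sidedness matters more than moderate attrition.

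These sizes rest on three assumptions that the documents do not settle: the loss rate, the test behind 398, and no gain from baseline adjustment. Such a gain could offset part or all of the loss (one-tailed at 20% loss: .756 if r=.3, .824 if r=.5). The treatment comparison is not made invalid by any of this. What lacks support is reading .80 as the power of a trial that enrols 400. It should be corrected, because the SAP itself foresees attrition and the correction is cheap.

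**What to change.** Amend the SAP's power paragraph to:

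1. label 398 as the number needed with T1 outcome data;
2. name the test and state whether it is one- or two-sided;
3. state one expected T1 retention;
4. restate the power for 400 randomised at that retention, either unadjusted or for the planned GEE with a stated baseline–T1 correlation.

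Suggested wording: *N=398 is the number of participants with T1 outcome data needed for power .80 (g=.25, alpha=.05, [test], [one- or two-sided]). We will randomise 400 and expect [x]% to provide T1 data ([n] observed), giving power [p] [unadjusted / for the GEE with baseline–T1 correlation r].*

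The cost is a few sentences and, probably, a less favourable stated power. No added enrolment is required. If the sponsor prefers to keep 398 observed, the number to randomise is 398/(1 − loss): 398/.95 = 418.9, 398/.90 = 442.2 and 398/.80 = 497.5, so 419, 443 or 498. That is 19, 43 or 98 more than planned at 5, 10 or 20% loss.
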